Study Periods/Duration	
The study will comprise a [REDACTED] Treatment Period and a Post-healing Follow-up Period of [REDACTED] both of which are double-masked.
 
Once determined to be eligible, subjects will be randomized to receive either NEXAGON [REDACTED] or NEXAGON [REDACTED] or Vehicle in a [REDACTED] ratio respectively. Investigational product will be applied [REDACTED]
 
[REDACTED] during the Treatment Period:
 
[REDACTED] [REDACTED] [REDACTED] [REDACTED]
 
However, if by [REDACTED] of the Treatment Period the cornea has not fully re-epithelialized, irrespective of the investigational product assignment at randomization, subjects will enter the open-label section of the study and will receive [REDACTED] applications of NEXAGON [REDACTED] NEXAGON [REDACTED] will be applied [REDACTED]. Subjects receiving salvage therapy will be followed from the first salvage dose application to determine if re-epithelialization occurs [REDACTED].
 
For each subject, the [REDACTED] masked Treatment Period will end when EITHER, corneal re-epithelialization is [REDACTED] recorded following up to a maximum of [REDACTED] applications of investigational product OR subjects enter the open-label section of the study as a result of an unhealed PED [REDACTED].
 
Those subjects who achieve re-epithelialization will immediately begin the [REDACTED] Post-Healing Follow-up Period. No further investigational product will be applied. The aim of the post epithelialization follow-up period is to assess the durability of the epithelium.
 
For those subjects that achieve re-epithelialization but epithelialization is NOT sustained during the [REDACTED] Post-healing Follow-up Period, the subject will become eligible to receive the salvage dose(s) of NEXAGON [REDACTED] and enter the open-label section of the study [REDACTED]. If re-epithelialization is not achieved [REDACTED] a second dose of NEXAGON [REDACTED] will be applied. If re-epithelialization occurs [REDACTED], a final assessment of the epithelium durability will be performed [REDACTED].
 
Subjects will also exit the study if re-epithelialization is not achieved [REDACTED] in the open-label section of the study.
 
The MAXIMUM duration for study participation for a subject is [REDACTED]

-------------------------------	---

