**Treatment Period (Masked):**

During the Treatment Period, masked investigational product will be administered on [REDACTED]

- If re-epithelialization of the defect has NOT occurred [REDACTED] another single application of masked investigational product will be administered [REDACTED]
- If re-epithelialization occurs at any time during the masked Treatment Period, subjects will enter a [REDACTED] Post-healing Follow-up Period to assess durability of the corneal epithelium.

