#### 5. Sample Size and Power Considerations

Assuming the true rate of corneal epithelialization in each of the NEXAGON arms of [REDACTED]  
[REDACTED]  
[REDACTED]

Assuming a discontinuation rate [REDACTED]

[REDACTED] Enrollment will continue until [REDACTED]  
[REDACTED]

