### 8.3 Definition of Baseline and Final On-Treatment Visit

Baseline will be defined as the last measurement prior to the first dose of study medication. Change from baseline will be calculated as follow-up visit value minus baseline value.

The final on-treatment visit is defined as the day of initial corneal re-epithelialization, treatment [REDACTED] or day of discontinuation during treatment.

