## 15. Safety Analyses

All safety analyses will be conducted using the safety population. Summaries of safety measures during the masked treatment and follow-up periods [REDACTED] will be completed similarly.

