Separate summaries of TEAEs will be provided showing the number and percentage of subjects who experienced at least one TEAE by treatment group and over all subjects. Non-ocular TEAEs will be summarized using discrete summary statistics and presented by treatment group at the subject and event level by SOC and PT. Ocular TEAEs will be similarly summarized at the subject level for study and fellow eyes separately. If a subject reports the same PT multiple times within the same SOC, that PT will only be reported once within that SOC. As with the PT, if a subject reports multiple conditions within the same SOC, that SOC will only be reported once. In the summary, SOCs will be listed in ascending alphabetical order; PTs will be listed in order of descending frequency for all subjects within each SOC.

The number of subjects with any TEAEs (along with percentages) will be tabulated by SOC and PT within each SOC by treatment group. Summaries of TEAEs by maximal severity, strongest relationship to study drug, and strongest relationship to study drug and maximal severity will be presented for ocular AEs and non-ocular AEs separately. To count the number of subjects with any TEAEs, if a subject has multiple TEAEs coded to the same PT within the same SOC, the subject will be counted once under the maximum severity. TEAEs that led to test article discontinuation, defied as drug interruption or drug withdrawal as response to the AE, treatment related TEAEs, and TE-SAEs will also be summarized by SOC and PT.

15.2

[REDACTED]

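### Masked observation time depends on healing, but the legible TEAE plan gives only counts and percentages by arm, so crude TEAE percentages can differ between arms at equal risk.

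*SAP*

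**What the plan says.** **How long a subject is observed.** The Protocol Synopsis (Study Periods/Duration) ends masked treatment in one of two ways: at re-epithelialization, or when "subjects enter the open-label section of the study as a result of an unhealed PED". On healing, the Synopsis continues, "Those subjects who achieve re-epithelialization will immediately begin the" Post-healing Follow-up Period, and "No further investigational product will be applied". SAP 3.1 has the same rule: "If re-epithelialization occurs at any time during the masked Treatment Period, subjects will enter a" follow-up period to assess durability. Protocol 4.1 keeps the masking during that follow-up. If the healed epithelium breaks down, the subject goes to open-label salvage. Unhealed subjects get open-label NEXAGON whatever their randomized arm. All period lengths are redacted.

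**Which time the TEAE tables cover.** SAP 15.1 and Protocol 9.1 record AEs from first application to the final visit, which is not a fixed day. SAP 15 refers to "Summaries of safety measures during the masked treatment and follow-up periods", and the words that follow are redacted. Protocol 10.2.8 summarizes open-label safety similarly for subjects who enter salvage.

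**How TEAEs are summarized.** SAP 15.1 is almost fully legible. The overall table gives the number of events and the number and percentage of subjects with a TEAE. Later tables show the "number and percentage of subjects who experienced at least one TEAE by treatment group and over all subjects", and frequency and percentage by system organ class and preferred term. No subject-time denominator, time to first TEAE or common window appears. Exposure has its own section (SAP 12) and table (14.3.9.6), with no visible link to TEAEs.

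**The concern.** A percentage of subjects with at least one event rises with the time each subject is watched. Here that time is set by healing, which is what NEXAGON is meant to change. If it works, the active arms hold more subjects with time to healing plus follow-up, and the Vehicle arm holds more with the full Treatment Period. Equal risk per day can then yield unequal percentages.

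Incidence of TEAEs is the only safety endpoint that the protocol and SAP name, and Protocol 1.3 says that both concentrations are assessed against Vehicle. Readers will set the by-arm percentages side by side. A gap produced by observation time could pass for a safety signal, or could hide one.

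**Working it through.** The documents give no legible period length, healing rate, TEAE rate or sample size, so there is no planned figure to reproduce. Every number below is an assumption, used to show direction and range.

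**Simple model.** Treatment Period T days, follow-up F days, healing at day h, TEAE hazard λ per day in every arm, probability of healing p. A healer is observed for h + F days and a non-healer for T days. Relapse and dropout are left out.

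- Mean masked time = p(h + F) + (1 - p)T
- Crude incidence = p[1 - exp(-λ(h + F))] + (1 - p)[1 - exp(-λT)]
- NEXAGON minus Vehicle = (p_N - p_V)[exp(-λT) - exp(-λ(h + F))]

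**Central case:** T = 28, F = 28, h = 14, healing 30% on Vehicle and 60% on NEXAGON. Healers are observed for 42 days and non-healers for 28.

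- Mean time, Vehicle: 0.3 × 42 + 0.7 × 28 = 32.2 days
- Mean time, NEXAGON: 0.6 × 42 + 0.4 × 28 = 36.4 days
- λ = 0.01: 27.4% vs 30.3%; difference 0.3 × (exp(-0.28) - exp(-0.42)) = +3.0 points
- λ = 0.02: 47.1% vs 51.2%; difference 0.3 × (exp(-0.56) - exp(-0.84)) = +4.2 points

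**Range** over T = 28 or 56, F = 14, 28 or 56, h = 7, 14 or 21, λ = 0.01 or 0.02:

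- Highest (T = 28, F = 56, h = 21, λ = 0.02): 0.3 × (exp(-0.56) - exp(-1.54)) = +10.7 points
- Lowest (T = 56, F = 14, h = 7, λ = 0.02): 0.3 × (exp(-1.12) - exp(-0.42)) = -9.9 points
- Zero when h + F = T, for example 14 + 14 = 28

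With a rarer event (λ = 0.002, as might suit related or serious TEAEs), the central case is 0.3 × (exp(-0.056) - exp(-0.084)) = +0.8 points and the grid runs from -1.9 to +2.6.

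**Check with variable healing times.** A simulation of 400,000 subjects per arm used exponential healing times, healing of 0.3 vs 0.7 or 0.2 vs 0.6, F from 7 to 56 days, and the same constant hazard in both arms (30% or 50% with an event per 28 days). Differences are NEXAGON minus Vehicle.

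| Period counted | Difference, points |
|---|---|
| Masked treatment only, T = 28 | -7 to -12 |
| Masked treatment only, T = 56 | -11 to -16 |
| Masked treatment plus masked follow-up | -12 to +12 |
| To final visit, with 28 days open-label | -17 to +2 |

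In the third row the sign depends on F. With T = 28, healing 0.3 vs 0.7 and the 50% hazard, F = 14 gives 49.6% vs 46.9% (-2.7), while F = 28 gives 53.9% vs 58.0% (+4.1). Mean observation is equal where F = (difference in mean treatment time) / (difference in healing): (23.6 - 16.3)/0.4 = about 18 days for this T and these healing rates, and 34 to 36 days if T = 56.

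**Does the remedy remove it?** Subjects with a TEAE divided by time at risk, per 28 days, came out about 0.36 in both arms at the 30% hazard and about 0.69 in both at the 50% hazard, in every scenario and period. This holds under a constant hazard.

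**Where a rate misleads.** Suppose instead that all events occur at dosing and 20% of subjects in each arm have one. Crude incidence is then equal and correct. On the central case's total masked days the rate is 20/32.2 = 0.62 vs 20/36.4 = 0.55 per 100 days, about 12% lower on NEXAGON with no difference in risk.

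**The case against.** The strongest reply has five parts.

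- **No comparison is planned.** The documents speak of comparing each dose with Vehicle for efficacy outcomes. TEAEs are summarized by treatment group, and no TEAE test is legible. This stands: a reader might infer a formal safety comparison, and the text does not contain one. Descriptive percentages by arm still carry the distortion.
- **The size is assumed.** This stands. The range spans zero, its ends are corner cases at the higher hazard, and the hazards have no source in the documents. The model also omits relapse, which shortens a healer's masked time, and the redacted window for assessing TEAEs after the final application.
- **A constant hazard is doubtful.** Applications are few and none follows healing. Protocol 1.2.2 reports transient stinging, tingling or burning on administration to chronic venous ulcers as the only possibly related events so far. This stands, and it is why rates should not replace percentages.
- **Redacted text may already deal with it.** Most of SAP 12, part of SAP 15 and all of 15.2 are hidden, and the table list has gaps. An adjusted table cannot be excluded. But SAP 15.1, where the TEAE methods are set out, shows no adjustment and no reference to one.
- **It is partly handled.** Exposure is tabulated, event counts accompany percentages, open-label safety is summarized separately, and SAP 15.1 provides for TEAEs before rescue medication. These help a reader, but the last changes which events count, and none relates TEAEs to time at risk.

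A reader might also infer that AEs are sought less often after healing, since the Synopsis sets twice-weekly visits only until re-epithelialization. Post-healing visit frequency is redacted, so this cannot be shown.

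**Conclusion.** The point holds in limited form. Masked observation time is a function of healing, and the legible TEAE plan makes no allowance for it. If healing rates differ, crude TEAE percentages are not strictly comparable between arms.

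It is tempting to go further and say that an effective arm and Vehicle will differ in TEAE incidence. The documents do not support that. Shorter treatment in healers is offset, wholly or in part, by follow-up that only healers have, and the lengths that decide the balance are redacted. The gap may be near zero. The sizes shown rest on assumed period lengths, healing rates and an equal constant hazard, and should be read as what could happen.

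The change is worth making before unmasking, so that the time-at-risk definition is not chosen with the results in view.

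**What to change.** In SAP 15.1:

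1. Keep the planned counts and percentages.
2. State for each by-arm TEAE table which periods it covers: masked treatment, masked follow-up, open-label.
3. For overall, study-eye ocular, related and serious TEAEs, add as supportive rows:
   - masked subject-time at risk, from first application to first salvage dose or masked exit, with the exposure-adjusted rate (for a first-event rate, time also stops at the first event);
   - Kaplan-Meier cumulative incidence of first TEAE through a common study day, censored at first salvage dose or masked exit. The day should be no later than the end of the masked Treatment Period, since beyond it only healed subjects remain under masked observation.
4. Say that by-arm differences will be read from the percentages together with these measures. Note that the rate assumes a roughly constant hazard and can mislead if events cluster at dosing, and that Kaplan-Meier censoring is tied to healing, so it assumes similar TEAE risk in healed and unhealed eyes.

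The cost is SAP wording and a few table rows. Application, visit and onset dates are already needed for the exposure, administration and AE outputs, so conduct does not change. If the redacted sections already contain one of these measures, a cross-reference from SAP 15.1 is enough for that part.

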5.2. Inclusion Criteria

A subject will be eligible for inclusion in this study only if ALL of the following criteria apply:

1. Male and female of any age.
2. Clinically non-infected, corneal persistent epithelial defect (PED) as a result of a severe chemical and/or thermal ocular injury in one or both eyes.
3. [REDACTED]
4. [REDACTED]
5. Providing written informed consent and ability to comply with the visit and dosing schedule.

NOTES:

- [REDACTED]
- [REDACTED]
- [REDACTED]
- [REDACTED]

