7.2. Dosage

Each investigational product and Vehicle dose application to the study eye will comprise of [REDACTED]

No topical ocular drops or ointment standard of care treatment will be permitted [REDACTED] following investigational product administration.

Investigational product will be applied on [REDACTED]

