The relationship of each AE or SAE to the study drug should be determined by the Investigator using these explanations: definitely related, probably related, possibly related, unlikely to be related, and unrelated. Only definitely, probably, and possibly related TEAEs will be considered as treatment-related TEAEs. For TEAEs prior to rescue medication use, only those TEAEs with an onset date prior to the date that rescue medications were first used will be included.

Clinically significant abnormal laboratory findings or other abnormal assessments that are present at baseline and significantly worsen following the start of the study will be reported as AEs and SAEs. The Investigator will exercise his/her medical and scientific judgment in deciding whether an abnormal laboratory finding or other abnormal assessment is clinically significant.

Verbatim descriptions of AEs will be mapped to MedDRA [REDACTED] terms and presented in a data listing. Adverse events recorded in the eCRF which began prior to treatment will not be included in the summary tables but will be included in the AE data listings. All AEs, SAEs, and TEAEs will be presented separately in subject data listings. The TEAEs leading to study treatment discontinuation will also be listed separately.

An overall summary will be presented that includes the number of events and the number and percentage of subjects who experienced at least one TEAE, by treatment group and over all subjects. This summary will also include breakdowns of TEAEs further categorized as ocular (study eye and, for subjects with bilateral injury, fellow eye separately) or non-ocular, treatment-related TEAEs, TE-SAEs, TEAEs leading to treatment withdrawal, TEAEs leading to death, TEAEs by maximal severity, and TEAEs by relationship to study drug.

Treatment-emergent adverse events (TEAEs), those that occur after the first dose of study medication, will be summarized by treatment group using frequency and percentages for each SOC and PT within each SOC. Similar summaries will be presented for treatment related TEAEs, TEAEs by maximum severity, serious TEAEs, and TEAEs leading to test article discontinuation.

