## 20. Tables for Final Analysis

Tables that will be included in the topline delivery are shown in boldface font.

Table Number	Title	Population
14.1.1	Subject Disposition	All Randomized Subjects
14.1.2.1.1	Demographic Characteristics	All Randomized Subjects
14.1.3.1	Ocular Medical History	Safety Population
14.2.1.1	Corneal Epithelial Recovery [REDACTED]	Full Analysis Set

14.3.1	Overall Summary of TEAEs by Treatment Group	Safety Population
14.3.2.1	Ocular TEAEs by System Organ Class and Preferred Term (Study Eye)	Safety Population
14.3.6	TEAEs That Led to Premature Test Article Discontinuation	Safety Population

14.3.7	Treatment-Related TEAEs	Safety Population
14.3.8	Treatment-Emergent Serious Adverse Events	Safety Population
14.3.9.1	Ocular Injury Questionnaire - Physician Assessment	Safety Population
14.3.9.3	PED Measurements	Safety Population
14.3.9.6	Exposure to Study Drug	Safety Population
14.3.10.1.1	Clinical Laboratory Measures - Hematology	Safety Population
14.3.10.1.2	Clinical Laboratory Measures – Shift in Hematology	Safety Population
14.3.10.2.1	Clinical Laboratory Measures - Chemistry	Safety Population
14.3.10.2.2	Clinical Laboratory Measures – Shift in Chemistry	Safety Population

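### SAP 15.1 splits ocular TEAE incidence by eye but not the severity, relationship, serious, treatment-related and discontinuation summaries, so fellow-eye events can be counted with study-eye events there

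*SAP*

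**What the plan says.** SAP 15.1 separates the eyes in two places.

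- **Incidence by system organ class (SOC) and preferred term (PT):** "Ocular TEAEs will be similarly summarized at the subject level for study and fellow eyes separately". Table 14.3.2.1 in SAP 20 is accordingly labelled for the study eye.
- **Overall TEAE summary:** events are "categorized as ocular (study eye and, for subjects with bilateral injury, fellow eye separately) or non-ocular". Treatment-related events, serious events, severity and relationship then follow as further items.

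The split is not carried into the remaining summaries.

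- **Maximal severity, strongest relationship, and the two crossed:** "strongest relationship to study drug and maximal severity will be presented for ocular AEs and non-ocular AEs separately".
- **Treatment-related, serious and discontinuation TEAEs:** "treatment related TEAEs, and TE-SAEs will also be summarized by SOC and PT", in a sentence that begins with the discontinuation events. Tables 14.3.6, 14.3.7 and 14.3.8 name no eye; the last is titled only "Treatment-Emergent Serious Adverse Events".
- **Counting rule for repeated events of one PT within one SOC:** "the subject will be counted once under the maximum severity". No eye is mentioned.

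Two design facts make the split relevant. Protocol 7.2 describes each "dose application to the study eye", and Protocol 5.2 admits "severe chemical and/or thermal ocular injury in one or both eyes". Protocol 4.1 allows only one study eye per subject with bilateral injury.

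**The concern.** The local safety question is whether topical NEXAGON harms the eye it is put on. A subject with bilateral injury brings a second injured eye, and the plan looks at it. Protocol 6.7.4 has slit-lamp examination of both eyes, and Appendices 2, 3 and 8 extend the symptom, pain and injury assessments to the fellow eye in bilateral injury. Worsening of an existing condition counts as a TEAE (Protocol 9.1.1), and sight-threatening events count as serious (Protocol 9.2). Deterioration of the fellow eye can therefore enter the severity and serious-event tables on the same footing as an event in the study eye.

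Two things follow. Background events added to every arm make the arms look more alike in severity and seriousness. In addition, a chance imbalance in bilateral injury between arms could look like a difference in severity between treatments, or hide one.

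**Working it through.** The documents state no event rates, bilateral share or visible sample size, so there is no plan figure to reproduce. The check has two parts.

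**1. The text, side by side**

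| Summary | Eye split stated in visible text |
|---|---|
| Overall TEAE summary | Yes |
| Ocular TEAEs by SOC and PT | Yes |
| Maximal severity | No, ocular or non-ocular only |
| Strongest relationship | No, ocular or non-ocular only |
| Relationship by severity | No, ocular or non-ocular only |
| Treatment-related (14.3.7) | No |
| Treatment-emergent serious (14.3.8) | No |
| Led to discontinuation (14.3.6) | No |

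Now apply the counting rule to one subject with a mild study-eye event and a severe fellow-eye event of the same PT. Read literally, the ocular severity table counts that subject once, as severe. The study eye contributed only the mild event.

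**2. The size, under assumptions**

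Let p be the study-eye risk in an arm and q the fellow-eye risk averaged over all subjects in that arm. Assume q is the same in every arm and the eyes are independent within a subject.

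- Pooled risk = 1 − (1 − p)(1 − q)
- Pooled risk difference = (1 − q) × study-eye risk difference

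With assumed study-eye risks of 30% on active and 10% on Vehicle:

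| q | Active pooled | Vehicle pooled | Difference (points) | Ratio |
|---|---|---|---|---|
| 0 | 30.0% | 10.0% | 20.0 | 3.00 |
| 2% | 31.4% | 11.8% | 19.6 | 2.66 |
| 5% | 33.5% | 14.5% | 19.0 | 2.31 |
| 10% | 37.0% | 19.0% | 18.0 | 1.95 |
| 20% | 44.0% | 28.0% | 16.0 | 1.57 |
| 30% | 51.0% | 37.0% | 14.0 | 1.38 |

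For rarer severe events, assume study-eye risks of 15% and 5%. Write q = b × f, where b is the share of subjects with bilateral injury and f is the fellow-eye risk among them, taken as 10% to 20%.

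| b | q | Difference (true 10 points) | Ratio (true 3.0) |
|---|---|---|---|
| 20% | 2% to 4% | 9.8 to 9.6 | 2.4 to 2.1 |
| 40% | 4% to 8% | 9.6 to 9.2 | 2.1 to 1.7 |
| 60% | 6% to 12% | 9.4 to 8.8 | 1.9 to 1.5 |

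The difference thus loses 2% to 12% of its size in these cases. The ratio loses more because the same background is added to both arms.

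For imbalance, suppose there is no drug effect: study-eye risk is 5% in both arms and f = 15%, but b is 40% in one arm and 20% in the other. Then q is 6% and 3%. The pooled risks are 1 − 0.95 × 0.94 = 10.7% and 1 − 0.95 × 0.97 = 7.85%, an apparent difference of 2.85 points that comes only from bilateral injury.

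For the treatment-related table, q includes only fellow-eye events that the investigator judges at least possibly related. Its effective value there should be well below the value for severe or serious events.

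**The case against.** A reader might infer that the plan dilutes any local drug signal. The documents do not support that. Study-eye incidence by SOC and PT is tabulated on its own, and the overall summary separates the eyes. The loss is confined to the secondary breakdowns.

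Other points against the concern have weight:

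- The overall-summary sentence could be read as crossing eye with severity, relationship and seriousness. It reads more naturally as a list of parallel items, and it does not govern the SOC and PT tables.
- The visible table list runs from 14.3.2.1 to 14.3.6. Titles of severity and relationship tables cannot be checked and might carry an eye label. The point therefore rests on the unredacted sentences of 15.1 and on the visible titles 14.3.6 to 14.3.8.
- Text next to the one-study-eye rule is redacted, as is the body of the fellow-eye analysis (SAP 14.5). It is safe to say that masked product goes to the study eye. It is not safe to describe everything that happens to the fellow eye.
- Causality assessment filters the related-event tables, and existing fellow-eye injury is a TEAE only if it worsens. No figure shows that fellow-eye events would dominate the serious-event table.
- The visible text describes these tables as counts and percentages, with no between-arm test. On the difference scale the attenuation may be small.
- Adverse events, including serious ones, are also listed by subject (listings 16.2.7.1 to 16.2.7.3), so case review is possible. The visible text does not confirm that the listings show the eye.

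These points limit the scope and leave the size unknown. They do not explain why 15.1 splits by eye for incidence and stops doing so where severity and seriousness are judged.

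**Conclusion.** The point holds as a gap in descriptive safety reporting. Following SAP 15.1 as written, fellow-eye events can be counted with study-eye events, mainly in the severity and serious-event tables and less so in the related-event tables. This attenuates or confuses the study-eye comparison of severity and seriousness. It does not remove the local signal, and it does not touch the primary efficacy analysis.

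The documents cannot settle the size. If the fellow-eye rate is q in every arm and independent of the study eye, the risk difference shrinks by the factor 1 − q and the ratio falls further; at q = 0 there is no loss. Every rate used in the check is an assumption. If the eyes are correlated, or q differs between arms, the simple factor no longer applies.

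**What to change.** In SAP 15.1 and the table list in SAP 20:

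- Present TEAEs by maximal severity, by strongest relationship and by the two crossed, and the treatment-related, serious and discontinuation TEAEs, in three blocks: study eye, fellow eye and non-ocular.
- State that the once-per-PT, maximum-severity and strongest-relationship rules apply within each eye.
- State that local safety is read from the study-eye block.

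The SAP already plans eye-specific TEAE summaries, so no new data should be needed. The cost is a few lines of wording, some extra tables and smaller counts per block.
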